## 4.2.8.4. Laboratory parameters

Clinical laboratory values as "<X" where X is the numerical value of the limit of quantification (LOQ) established by the laboratory will be imputed by LOQ/2 for summaries in the tables.

Clinical laboratory values as ">X" where X is the numerical value of the limit of quantification (LOQ) established by the laboratory will be imputed by LOQ for summaries in the tables.

Laboratory data below the lower limit of quantification (BLQ) should be labelled as such in the data listings.

#### 4.2.8.5. Missing and partially missing dates

For identification of AEs as treatment-emergent, partial or missing dates for adverse events will be imputed as follows:

- Incomplete start date: if the day and month are missing and year is the same as first drug administration, or if only the day is missing and month and year are the same as first drug administration then the start date will be replaced by the minimum between first drug administration and AE resolution date. In all other cases the missing start day or start month will be replaced by 01.
- Complete missing start date: the start date will be replaced by the minimum between first drug administration and AE resolution date.
- Incomplete stop dates (Month and year available or only year available): these dates will be imputed to the last day of the corresponding month, or the last day of the corresponding year if not resulting in a date later than the date of subject's death. In the latter case the date of death will be used to impute the incomplete stop date. In all other cases the incomplete stop date will not be imputed.

For medications and procedures, imputation of missing or partial dates will be done to identify concomitant medications and procedures as follows:

- If the start date of the medication/procedure is unknown (i.e. complete missing date), the worst-case scenario will be assumed. The medication/procedure will be considered as both a prior medication/procedure and a concomitant medication/procedure (i.e. the medication will be assumed to start on January, 1st 2016).
- If the month and the day of the start date of the medication/procedure are missing, the month and the day will be imputed to January, 1st of the year specified.
- If the day of the start date of the medication/procedure is missing, the day will be imputed to the first day of the month specified.
- If the end date is unknown (i.e. missing), the date will be kept as missing however the medication/procedure will be considered concomitant.
- If the month and the day of the end date of the medication/procedure are missing, the month and the day will be imputed to December, 31st of the year specified.
- If the day of the end date of the medication/procedure is missing, the day will be imputed to the last day of the month specified.

For disease history, imputation of missing or partial dates (date of onset of CKD and date of first dialysis) will be done as follows:

- If the month and the day of the date are missing, the month and the day will be imputed to January, 1st of the year specified.
- If the day of the date is missing, the day will be imputed to the first day of the month specified.
- In case of missing date, no imputation will be performed.

No other dates will be imputed.

The original incomplete, missing or partial dates will be presented in the listings, not the imputed dates.

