#### 1. INTRODUCTION AND OBJECTIVES OF ANALYSIS

#### 1.1. Introduction

Hyperphosphataemia (HP) is a common and serious complication in subjects with chronic kidney disease (CKD), particularly those with end-stage renal disease (ESRD) requiring dialysis. In the paediatric population, CKD is most commonly caused by congenital anomalies of the kidney and urinary tract such as aplasia/hypoplasia/dysplasia and obstructive uropathy. The frequency of such conditions is low. Glomerular diseases of various aetiologies, (e.g., polycystic kidneys, pyelonephritis) can also cause CKD, but with a lower frequency. HP plays an important role in the pathophysiology of major CKD complications for example secondary hyperparathyroidism, renal bone disease and cardiovascular disease, and appears to promote the progression of CKD towards ESRD. High levels of serum phosphorus are considered to be a risk factor for mortality, morbidity and hospitalisation in patients with ESRD.

Complications most relevant to the paediatric population are renal bone disease, also called renal osteodystrophy (sometimes referred to as mineral bone disease), cardiovascular disease and growth failure.

As the efficacy and safety of PA21 has been confirmed in adult subjects with CKD on dialysis, the aim of this Phase 3 clinical study is to demonstrate similar efficacy of PA21 in paediatric and adolescent subjects with CKD, and to provide safety and dosing information for this subject population. The Phoslyra group provides information for a descriptive comparison of PA21 against a commonly used calcium-based phosphate binder (calcium acetate).

This Statistical Analysis Plan (SAP) has been developed for the final analyses of protocol PA-CL-PED-01 (Version 2.0, 22 September 2015), prior to final database lock. It outlines the efficacy and safety analyses, including tables, listings, and graphical presentations to be included in the Clinical Study Report (CSR). A complete draft SAP has been developed and approved by the sponsor statistician before any significant accumulation of data.

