#### 4.5.2. Baseline Disease Characteristics

Summary statistics will be provided for baseline disease characteristics including reason or cause of CKD, CKD stage, time since onset of CKD (years), time since first dialysis (years), baseline type of dialysis (haemodialysis, peritoneal dialysis, none), PB naïve (yes/no), Washout period needed (yes/no), baseline serum phosphorus (central laboratory in both Standard and Conventional units).

Time since onset of CKD (years) will be derived as: (date of informed consent - date of onset of CKD + 1)/365.25

Time since first dialysis (year) will be derived as: (date of informed consent - date of first dialysis +1/365.25

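### SAP 4.2.8.5 imputes partial dates of CKD onset and first dialysis to the earliest possible day with no plausibility bound, so onset can precede birth and first dialysis can precede onset

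*SAP*

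**What the plan says.** SAP section 4.2.8.5 has a separate rule for disease history: "imputation of missing or partial dates (date of onset of CKD and date of first dialysis) will be done as follows". The rule has three parts:

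- Year only: "If the month and the day of the date are missing, the month and the day will be imputed to January, 1st" of the recorded year.
- Month and year: "If the day of the date is missing, the day will be imputed to the first day of the month specified".
- Nothing recorded: "In case of missing date, no imputation will be performed".

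None of the three refers to date of birth, to the other disease-history date or to consent.

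Section 4.5.2 then uses the date without any further check: "Time since onset of CKD (years) will be derived as: (date of informed consent - date of onset of CKD + 1)/365.25". Time since first dialysis is built the same way. Both are baseline disease characteristics. Under section 4.5 and the table list in 7.1 they are summarised for four populations, overall and by age, gender and region (Tables 14.1.5.1 to 14.1.5.16).

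Section 1.1 says of the paediatric population that "CKD is most commonly caused by congenital anomalies of the kidney and urinary tract".

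**The concern.** The first of January is the earliest day that a year-only date can represent. Using it for a continuous duration errs in one direction: the duration is either exact or too long. In children this can also produce an impossible value. With congenital disease, the birth year is a natural entry for year of onset, and every birthday except 1 January then lies after the imputed onset. The baseline table would report a disease duration longer than the child's life.

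The two disease-history dates can also fall in the wrong order, because each is imputed without reference to the other.

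Bounds of this kind are already used elsewhere in the same section. An imputed adverse event start date is limited by the resolution date, and an imputed stop date by the date of death. The disease-history rule has no such limit.

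What is at stake is the credibility of two reported baseline characteristics, not an efficacy or safety conclusion.

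**Working it through.** The SAP gives no figure on this point, so there is nothing to reproduce. The check applies the rule in 4.2.8.5 to the formula in 4.5.2.

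**One record (illustrative dates).** Born 20 October 2014, onset recorded as 2014 only, consent 15 March 2017.

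- Imputed onset: 1 January 2014, which is 292 days before birth.
- Time since onset: (1169 + 1)/365.25 = 3.20 years.
- Age at consent: 877/365.25 = 2.40 years.
- With onset floored at birth: (877 + 1)/365.25 = 2.40 years. The only remaining excess over age is the formula's own extra day (0.003 year).

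**All birth dates in a year.** Assume onset at birth, only the year recorded, and births uniform over a 365-day year. The excess in days runs over 0, 1, …, 364.

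- Imputed onset precedes birth for 364 of 365 birth dates.
- Mean excess: 182 days, and 182/365.25 = 0.50 year.
- Maximum: 364 days, and 364/365.25 = 1.00 year (365 days in a leap year).
- Month and year recorded: mean about 15 days, maximum 30 days.

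**Against the age that is tabulated.** Section 4.5.1 reports age at randomisation, not at consent. If consent is given at screening, the longest scheduled gap from Table 2, footnote 2 is 28 + 21 + 2 = 51 days. The derived time still exceeds the tabulated age when the excess plus one day is more than 51, that is for excesses of 51 to 364 days: 314/365 = 86% of birth dates.

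**Relative size for one affected record.** 0.5/4 = 12.5% of the maximum possible duration at age 4; 0.5/14 = 3.6% at age 14. The absolute shift is the same at both ages.

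**Shift in a cohort mean.** The share f of affected subjects is not stated, so a range is assumed. Shift = f × 0.498 year:

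| f | Shift (years) |
|---|---|
| 10% | 0.05 |
| 25% | 0.12 |
| 50% | 0.25 |
| 100% | 0.50 |

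The last row would need every subject to have a year-only onset at birth; it is a ceiling, not an expectation.

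**Order of the two dates (illustrative).** Onset fully dated 10 May 2015, first dialysis recorded as 2015 only. The imputed first dialysis is 1 January 2015, which is 31 + 28 + 31 + 30 + 9 = 129 days before onset. Time since first dialysis then exceeds time since onset by 129/365.25 = 0.35 year.

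**The case against.** The strongest reply is that nothing rests on these variables. Section 4.5 rules out formal comparisons of baseline data. Neither duration is a covariate in 4.2.4 or 4.7.1, a subgroup factor in 4.2.6 or a major deviation in 3.2. The SAP never derives the interval between onset and first dialysis. The listings show the dates as recorded, so a reader can see which are partial. First-of-period imputation is prespecified and matches the SAP's rule for medication start dates. All of this stands, and it sets the weight of the point. It does not remove the impossible values from the tables.

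Four stronger readings are tempting, but the SAP does not support them:

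- A reader might infer that every congenital case is dated before birth. That requires the recorded onset year to be the birth year. Section 1.1 describes the cause of CKD, not when its onset is recorded, and a child with a congenital anomaly may have a later onset year.
- A reader might infer that the typical record is affected. The number of year-only dates is not given.
- A reader might infer that the youngest children carry the largest error. Only the relative error is larger. The document history also notes, for one PA21 subgroup table, that the first age group has no subjects, so examples in infants may not arise in that group.
- A reader might infer that mid-year imputation is required. For onset at birth, 1 July would understate duration in children born from January to June, even with a floor at birth. The choice between first-of-period and mid-period is one of preference; the missing bound is the defect.

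**Conclusion.** The point holds as a minor defect. As written, the rule can give a time since CKD onset that exceeds the child's age and a first dialysis that precedes onset, and nothing else in the SAP prevents either result. For an affected record the excess averages about 0.5 year and can reach 1 year. That rests on a recorded onset year equal to the birth year, onset at birth, and births uniform over the year. Any other year-only date is also overstated or at best exact, but not impossible on that account.

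The effect on group means depends on a share of partial dates that the SAP does not give. It is confined to the descriptive baseline tables 14.1.5.x. The primary analysis, the secondary analyses and the subgroup definitions are unaffected.

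**What to change.** Add to section 4.2.8.5, for disease history:

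- Imputed CKD onset is the later of the date from the present rule and the date of birth. If the full birth date is not collected, use consent date minus age. If that age is in completed years only, the floor is approximate and should not move the date out of the recorded year or month.
- Imputed first dialysis is no earlier than CKD onset, provided the result still agrees with the recorded partial date. If the recorded year or month itself contradicts the onset date, that is a matter for a data query, not for imputation.

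The cost is one extra derivation that needs birth date or age. The SAP does not name date of birth as an analysis variable, so its availability should be confirmed first. Mid-period imputation is optional and not part of this change.

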#### 4.2.9. Visit Windows

The below windowing will be applied for summary tables with descriptive statistics over time, label of the visit will be derived as below.

Analysis visit	Week number	Windowing
Visit 5	Day 1 (Baseline) Stage 1	Day 1 (Visit 5)
Visit 6	Week 1 - Stage 1	Day 8 (+/- 3 days)
Visit 7	Week 2 - Stage 1	Day 15 (+/- 3 days)
Visit 8	Week 4 - Stage 1	Day 29 (+/- 3 days)
Visit 9	Week 6 - Stage 1	Day 43 (+/- 3 days)

Visit 10	Week 8 - Stage 1	Day 57 (+/- 3 days)
Visit 11	Week 10 - Stage 1	Day 71 (+/- 7 days)
N/A	Day 1 (Baseline) Stage 2	Day 1 (last visit in the titration phase + 1)
Visit 12	Week 4 - Stage 2	Day 29 (+/- 3 days)
Visit 13	Week 8 - Stage 2	Day 57 (+/- 3 days)
Visit 14	Week 12 - Stage 2	Day 85 (+/- 3 days)
Visit 15	Week 18 - Stage 2	Day 127 (+/- 7 days)
Visit 16	Week 24 - Stage 2	Day 169 (+/- 7 days)

If several values are falling into the same time window then the nearest value compared to the pre-defined week window as per protocol will be considered for efficacy and safety, if they are still 2 or more values then the first one in time among the nearest value will be considered. In case of 2 values at the same time (planned visit and unscheduled one), then the planned visit will be considered.

In addition, visit 11 or earlier (visit when "Yes" is responded to the question "Will subject enter the Stage 2 Safety Extension period after the current visit?") and visit 16 or earlier data will be reported with the corresponding label in the summary tables "End of Stage 1" and "End of Stage 2", respectively. If subject withdrew during stage 1, visit 16 will be displayed with the corresponding label in the summary tables "End of Stage 1".

For "End of Stage 1" and "End of Stage 2" reported visits of the safety analyses, the original visits (as collected in the EDC system and not derived) will be used. The last non missing assessment collected in each period will be reported under "End of Stage 1" and "End of Stage 2".

# 4.3. Interim Analyses

No interim analysis is planned for this study. A DSMB will review regularly the safety data to protect the safety of study participants. The procedures and analyses provided to DSMB are described in the DSMB Charter document.

# 4.4. Subject Disposition

Number of subjects treated at each site, country and region will be tabulated by treatment group and overall. A study populations table will describe the different populations used for analysis (FAS, PPS, Safety Population and Stage 2 Safety Population).

Subject disposition will be tabulated and will include the number of subjects randomised in Stage 1, the number of subjects treated, the number of subjects who enter the Stage 2, the number of subjects who completed the study, the number who withdrew prior to completing the treatment overall, during stage 1 and during stage 2, and reason(s) for withdrawal. The number of subjects who withdrew prior to completing the treatment overall, during stage 1 and during stage 2, and reason(s) for withdrawal will be also provided by age group. Summary data will be presented by treatment group and overall.

A by-subject listing of treatment completion information, including the reason for premature treatment withdrawal, if applicable, will be presented.

# 4.5. Demographic and Baseline Characteristics

Baseline, demographic, medical history and surgery history information will be summarised for the safety, Stage 2 safety, FAS and PPS Populations by treatment group and overall using descriptive statistics. No formal statistical comparisons will be performed.

Demographics and baseline disease characteristics will also be summarised by subgroups (age, gender, and region) for the safety, Stage 2 safety, FAS and PPS Populations.

Demographic and baseline data will be provided in data listings.

## 4.5.1. Demographics

Summary statistics will be provided for age at randomisation (years) as continuous and categorical variables (section 4.2.6; the 0 to <2 year category will be divided in two categories: 0 to <1 year and 1 to <2 year) and below), sex, race, ethnicity, region, baseline height (cm), baseline weight (kg), and baseline body mass index (BMI; kg/m²).

The following age categories will be considered:

- New borns (0-27 days)
- Infants and toddlers (28 days-23 months)
- Children (2-11 years)
- Adolescents (12-17 years)
- Adults (18-64 years)

#### 4.5.2. Baseline Disease Characteristics

Summary statistics will be provided for baseline disease characteristics including reason or cause of CKD, CKD stage, time since onset of CKD (years), time since first dialysis (years), baseline type of dialysis (haemodialysis, peritoneal dialysis, none), PB naïve (yes/no), Washout period needed (yes/no), baseline serum phosphorus (central laboratory in both Standard and Conventional units).

Time since onset of CKD (years) will be derived as: (date of informed consent - date of onset of CKD + 1)/365.25

Time since first dialysis (year) will be derived as: (date of informed consent - date of first dialysis +1/365.25

### 4.5.3. Medical History

Medical history will be coded using the Medical Dictionary for Regulatory Activities (MedDRA version 19.1 or later) and displayed in tables and listings using System Organ Class (SOC) and Preferred Term.

#### 4.5.4. Surgery History

Surgery history will be displayed in listing only.

## 4.6. Exposure to Study Drug

Exposure to study drug will be summarised for each drug separately and for stage 1, stage 2 and overall study using descriptive statistics. Summary tables will be generated on the Safety Population for stage 1 and overall study exposure and on the Stage 2 Safety Population for stage 2 exposure data. They will include:

## • For PA21 drug:

- o total number of tablets taken / total number of sachets taken,
- o actual average daily number of tablets taken / actual average daily number of sachets taken
- o actual average daily dosage (mg),
- o prescribed average daily dosage (mg),
- o duration of exposure (weeks),
- o compliance
- o maximum prescribed daily dose,
- o and reason of dose change.

#### • For Phoslyra drug:

- o actual average daily dosage (mL),
- o prescribed average daily dosage (mL),
- o duration of exposure (weeks),
- o compliance,
- o maximum prescribed daily dose,
- o and reason of dose change.

These tables for the PA21 group will be repeated by age group at randomisation, by gender, by region and by formulation (tablets only/sachets only/both).

The total and actual average daily number of tablets/sachets taken will be defined as

#### • For PA21 Drug:

Number of tablets/sachets dispensed – sum(Number of tablets/sachets returned or lost)

The actual average daily number of tablets/sachets taken will be defined as:

Total number of tablets/sachets taken / (last date of administration - start date of administration + 1)

The average daily dosage (g or mL) will be defined as

#### • For PA21 Drug:

(Total number of tablets/sachets taken  $\times$  strength in g PA21) / (last date of administration - start date of administration + 1)

## • For Phoslyra Drug:

(Total content of bottles taken) / (last date of administration - start date of administration + 1)

The prescribed average daily dosage (mg or mL) will be defined as:

 Note: Tablets may have different strengths.

 $\sum_{i=1}^{n}$  (end date - start date of administration(i) +1) \* Prescribed Total Daily dosage of administration(i)

last date administration - start date of administration + 1

i being the ith subject's administration and n the last subject's administration, i will be incremented from 1 until n by 1.

All subject's administrations will be considered for the overall study prescribed average daily dosage, whereas only subject's administration during the stage 1 or during the stage 2 will be considered for the prescribed average daily dosage for the stage 1 and for the stage 2, respectively.

Duration of exposure (days) for stage 1 will be defined as: (date of last administration in stage 1 (i.e. last administration until the last visit in the titration phase) – date of first administration in stage 1+1).

Duration of exposure (days) for stage 2 will be defined as: (date of last administration in stage 2–date of first administration in stage 2 (i.e. from the day after the last visit in the titration phase) +1).

Overall duration of exposure (days) will be defined as: (date of last administration in the study – date of first administration in stage 1+1).

Overall compliance (%) will be defined as:

- For PA21 drug: [[total number of mg corresponding to sachets/tablets dispensed (total number of mg corresponding to unused sachets/tablets returned + total number of mg corresponding to unused sachets/tablets reported as lost)]/ total prescribed dose (in mg)]\*100, where the total number of mg corresponds to the number of sachets/tablets \* the dosage of the corresponding sachets/tablets and the total prescribed dose corresponds to Σni=1 (end date start date of administration(i) +1) \* Prescribed Total Daily dosage of administration(i) (in mg) as defined earlier. The prescribed total daily dosage (in mg) from the PA21 dosing eCRF page will be considered.
- For Phoslyra drug:[[473\* total number of bottles dispensed (473\* total number of unused bottles + 473\* total number of bottles reported as lost + sum of mL left from the total number of partially used bottles returned)] / total prescribed dose (in mL)]\*100, where the total prescribed dose corresponds to ∑i=1n (end date start date of administration(i) +1) \* Prescribed dose of administration(i) (in mL/day) as defined earlier. The prescribed dose (in mL/day) from the Phoslyra dosing eCRF page will be considered. Of note for the partially used bottles, eCRF collect only millimetres left, the information from table 7 will be used to convert approximately the millimetres to millilitres. Each bottle will be assumed to contain 473mL, i.e. 139 millimetres. In case no kit/bottle is returned or all kits/bottles are declared as lost, the compliance will be considered as missing.

For patients with all dispensed tablets/sachets or bottles unused, reported as lost and no tablets/sachets or bottles returned dates, all exposure variables listed above excluding exposure durations and prescribed daily dose variables (maximum, average); and compliance will be set to missing.

For subjects who did not enter into Stage 2: all the records from the "Dispensation/Compliance" CRF Form will be assigned into Stage 1.

For subjects who entered into Stage 2: all the records from the "Dispensation/Compliance" CRF Form with a dispensed date < End of Stage 1 date -3 days will be assigned into Stage 1; the other records will be assigned into Stage 2.

Table 7 Approximate transformation from millimetres to millilitres to be used for Phoslyra compliance derivation

Phoslyra Bottle		
Millimetres (mm)	Millilitres (mL)	
139	473	
130	448	
120	411	
110	375	
100	339	
90	303	
80	268	
70	234	
60	200	
50	166	
40	130	
30	94	
20	59	
10	24	
1	1	

Linear interpolation will be used for millimetres not listed in table 7. The following formula will be applied:

 $mL = mL_0 + (mm - mm_0) * [ (mL_1 - mL_0)/(mm_1 - mm_0)]$ 

